6.7 Statistical analysis issues	
6.7.1 Multiple comparisons	
6.7.2 Multi-centre studies	30
6.7.3 Post-Hoc analysis	31
7. Safety analysis	
8. Additional analysis	
8.1 Additional analysis	32
9. Presentation of analysis	
References	
Appendix A: Deviations from the SAP	35

Abbreviations and Definitions

ACR	American college of rheumatology	
ANCOVA	Analysis of covariance	
AUC	Area under the curve	
CDAI	Clinical disease activity index	
CRP	C-reactive protein	
CSR	Clinical study report	
CTU	Clinical Trials Unit	
DAS	Disease activity score	
csDMARD	Conventional synthetic Disease Modifying Anti- Rheumatic Drugs	
EMR	Experimental Medicine and Rheumatology	
EQ-5D-5L	EuroQol- 5 Dimension Level 5	
EULAR	European League Against Rheumatism	
ESR	Erythrocyte sedimentation rate	
ESS	Epworth Sleepiness Scale	
FACIT	Functional Assessment of Chronic Illness Therapy	
FDC	Follicular dendritic cell	
HAQ	Health Assessment Questionnaire	
IQR	Interquartile range	
ISRCTN	International Standard Randomised Controlled Trial Number	
ITT	Intention to Treat	
MRC	Medical Research Council	
MTR	Major treatment response	
MTX	Methotrexate	
NICE	National Institute for Health and Care Excellence	
NIHR	National Institute for Health Research	
NRAS	National Rheumatoid Arthritis Society	
PI	Principal Investigator	
PPI	Patient and Public Involvement	

PP	Per protocol
QMUL	Queen Mary University of London
RA	Rheumatoid arthritis
SAF	Safety analysis set
SAE	Serious Adverse Event
SAP	Statistical Analysis Plan
SF-36	36-Item Short Form Survey (SF-36)
TNFi	Tumour necrosis factor inhibitor
US	Ultrasound
VAS	Visual Analogue Scale

1. Statistical analysis plan (SAP) authorship

The Trial Statistician is responsible for writing the Statistical Analysis Plan (SAP), writing the computer code for implementing the SAP at the point of analysis.

The Trial Manager and the Lead Trial Statistician will review the SAP. The Statisticians and the Chief Investigator will sign off the final SAP.

The SAP has been finalised prior to unblinded analysis. The SAP has been drafted by the Trial Statistician and approved by the Lead Statistician. The Trial Statistician will complete the randomisation checks, TSC reports (open reports) and complete the final trial analysis. If any changes are requested to the SAP during the trial, this should be confirmed and agreed in writing by the Lead Statistician and Independent Statistician. Following trial analysis, the primary analysis will be checked by the Lead Statistician or an independent Statistician (independent from the study team and has not been involved in any 3TR PARTNER-RA data analysis previously).

Blinding within the trial:

The participant nor any of the investigators or site staff who are involved in the treatment or clinical evaluation and monitoring of the participants will be aware of the study intervention received. The Chief Investigator and recruiting study site teams will be blinded to the arm that the patient has been allocated to (intervention or control arm).

This document is the SAP for the 3TR PARTNER-RA trial and should be read in conjunction with the current trial protocol. This SAP details the proposed analyses and presentation of the data for the main paper(s) reporting the results for the 3TR PARTNER-RA trial.

The results reported in these papers will follow the strategy set out here. Subsequent analyses of a more exploratory nature will not be bound by this strategy, though they are expected to follow the broad principles laid down here. The principles are not intended to curtail exploratory analysis (e.g. to decide cut-points for categorisation of continuous variables), nor to prohibit accepted practices (e.g. transformation of data prior to analysis), but they are intended to establish rules that will be followed, as closely as possible, when analysing and reporting data.

Any deviations from this SAP will be described and justified in the final report or publication of the trial (Appendix A). The analysis will be carried out by an appropriately qualified statistician, who should ensure the integrity of the data during their data cleaning processes.

2. Introduction

The 3TR PARTNER-RA trial is a double blinded, phase IV, randomised controlled, multi-centre, controlled Clinical Trial of an Investigational Medicinal Product (CTIMP) in a population of patients newly diagnosed with RA (symptoms <12 months) and fulfilling the 2010 ACR/EULAR classification criteria for RA who have an inadequate response to conventional Disease Modifying Anti-Rheumatic Drugs (DMARDs) and are eligible for anti-TNF therapy according to EULAR recommendations: treatment for ≥ 3 months with ≥ 1 csDMARDs¹. Patients recruited to this study will undergo a synovial biopsy at baseline and randomised (1:1) to drug (abatacept) and methotrexate or placebo and methotrexate arm. Patients will be followed up to 16 weeks at which point all patients will be offered a voluntary second synovial biopsy.

In recent years, thanks to the development of minimally invasive ultrasound-guided biopsy² synovial tissue analysis has been proposed as a tool for patient stratification with potential use in clinical practice. In patients with early RA, recent publications indicated that histological³ and molecular⁴ signatures in the synovial tissue are associated with disease outcomes and can stratify response to treatment and predict disease progression, including use of biologics⁵. Recently, the first biopsy-driven Randomised Clinical Trials in RA has shown that the lack of B cell lineage signatures in synovia is associated with lack of response to B cell depleting agent (rituximab) as compared to an alternative medication targeting IL6 receptor (Tocilizumab)⁶.

Patients will be randomised to either an intervention arm or control arm after having a synovial biopsy. If randomised to the intervention arm (treatment by biomarker), the patient's biopsy tissue will be analysed within 2 weeks. In the absence of a target biomarker the patient will be randomised 1:1 to either abatacept or placebo. If the patient is randomised to the control arm, they will be randomised again 1:1 to either Abatacept + MTX or placebo. Patients will continue trial treatment

until 16 weeks, where the treatment response will be assessed as the primary endpoint. There will be a post-treatment visit/call scheduled 30+ days after week 16 (Visit 7). Patients will attend 5 visits (Protocol: Study Schedule, Page 30).

The end of the study will be triggered up to a maximum of 4 months after the last patient completes their final study visit (Last Patient Last Visit-LPLV) at the post-treatment visit/call assessment 30+ days following completion of trial treatment (Protocol Section 13.1).

All joint assessments (Protocol Section 9.8) will be performed by a member of the local trial team who will be blinded to treatment allocation. All participating site staff will be blinded to the arm of the study the patient has been allocated to (Protocol Section 9.8).

The specific aim of the sub-study is to discover if a biopsy at presentation prior to any RA treatment (collected as part of the 3TR Early RA study) can be used to determine treatment response even after the patient has received cDMARDs.

2.1 Study objectives

Primary objective: The primary objective of this trial is to determine whether synovial molecular profiles (=drug target signatures) can inform treatment response to abatacept in early RA..

To this aim, we will compare the change in Clinical Disease Activity Index (CDAI) score at 16 weeks between the biomarker positive and the biomarker negative patients within the abatacept group (i.e. Group 1 vs Group 3) Fig.1 Study Scheme diagram. The primary trial hypothesis is that biomarker positive patients treated according to their highest expressed biomarker will have lower CDAI response at 16 weeks compared to biomarker negative patients.

[figure not shown]
This primary analysis has been chosen as we want to establish a difference in response rates in the treatment in the biomarker arm first, and the trial has been powered for this.

Secondary objectives:

The following analysis will be done:

- Compare patients treated according to their biomarker in the intervention arm against the control arm as a whole (i.e. Group 1 vs 3+4), to determine the enrichment in response in the treatment allocation arm vs the standard of care response rate.
- II. Assess the efficacy of treatment allocation according to biomarker compared to random allocation, we will compare the biomarker positive patients in the intervention arm vs the biomarker positive patients in the control arm (i.e. Group 1 vs Group 4)
- III. Assess the efficacy of the strategy as a whole against the current clinical practice by comparing the control vs intervention arm (i.e. Groups 1 + 2 vs Group 3+4)

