2.4 Randomisation

Randomisation will take place when all the screening procedures and the biopsy visit are completed, and the patient is eligible for enrolment in the study. The randomisation in the study will be applied using simple randomisation, with equal allocation ratio (1:1). All patients with sufficient RNA for analysis will be randomised using simple randomisation (1:1 allocation ratio) into the Control or the Treatment arm according to biomarker arm.

Patients allocated to the control arm of the study, will be subsequently randomised again using simple randomisation with equal treatment allocation ratio (1:1) to Abatacept and Methotrexate therapy or placebo and Methotrexate therapy.

Once the biopsy sample has been received by the central laboratory, patients will be stratified into 2 groups, CD80/CD86 positive (biomarker+) or CD80/CD86 negative (biomarker-) and randomised 1:1 to receive either Abatacept and Methotrexate therapy or placebo and Methotrexate therapy.

3. General Analysis Definitions

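### Secondary objective III: Groups 1+2 vs 3+4 has an expected difference of zero under SAP section 2.4, and under section 2 it cannot separate biomarker targeting from greater abatacept use

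*SAP*

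**What the plan says.** Objective III in section 2.1 is to "Assess the efficacy of the strategy as a whole against the current clinical practice by comparing the control vs intervention arm". The comparison it names sets Groups 1 and 2 together against Groups 3 and 4 together. Section 6.1.2 lists only two group comparisons for the secondary endpoints, and this is one of them. Section 6.7.1 sets a 5% level for primary and secondary analyses without multiplicity correction.

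The SAP describes the allocation twice.

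- **Section 2.4.** Patients are first randomised 1:1 "into the Control or the Treatment arm according to biomarker arm". Control patients are then "randomised again using simple randomisation with equal treatment allocation ratio (1:1) to Abatacept and Methotrexate therapy or placebo and Methotrexate therapy". After the biopsy has been received, "patients will be stratified into 2 groups, CD80/CD86 positive (biomarker+) or CD80/CD86 negative (biomarker-) and randomised 1:1 to receive either Abatacept" with methotrexate, or placebo with methotrexate. On this text both biomarker strata are split 1:1.
- **Section 2 (Introduction).** "If randomised to the intervention arm (treatment by biomarker), the patient's biopsy tissue will be analysed within 2 weeks". It continues: "In the absence of a target biomarker the patient will be randomised 1:1 to either abatacept or placebo". Nothing is said about how biomarker-positive intervention patients are treated. The label of the arm implies that all of them receive abatacept. The control arm is again split 1:1.

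The four groups are not defined consistently in the text. Objectives I to III treat 1 and 2 as the intervention arm and 3 and 4 as the control arm. The primary objective treats Groups 1 and 3 as biomarker-positive and biomarker-negative patients on abatacept. Section 2.3 places Groups 2 and 3 together as lacking the biomarker.

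**The concern.** A comparison of arms can show an effect of biomarker-guided treatment only if the biomarker changes who is treated with what. Under section 2.4 it changes nothing, because both arms give the same treatment mix to the same kind of patient. Under section 2 it changes treatment only by giving more abatacept to positives. The contrast then mixes two things: the benefit of using more of an active drug, and the benefit of directing it to the right patients.

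The stake is misreading. Under section 2.4 a null result could be reported as failure of the biomarker strategy, and a significant result would be a false positive. Under section 2 a positive result could be credited to the biomarker when it reflects wider use of abatacept. In both cases the comparator is labelled current clinical practice. It is in fact random allocation to abatacept or placebo, with methotrexate, in patients whom section 2 describes as eligible for anti-TNF therapy.

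**Working it through.** **The plan's own figure.** Section 2.3 gives a difference of 10, SD 14.34 and 90% power; section 6 sets a two-sided 5% level. The normal formula gives 2 × (1.960 + 1.282)² × 14.34² / 10² = 43.2, so 44 per group. The t-based calculation gives 44.2, so 45 per group and 90 in total, as stated. Four groups of 45 make 180, and 180 / 0.90 = 200. The plan's 90, 180 and 200 reproduce. The arm contrast therefore has about 90 evaluable patients per arm.

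**Notation.** Effects are counted as extra CDAI reduction.

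- p: prevalence of biomarker-positive patients. Not in the SAP; assumed 0.3 to 0.7. Equal groups of 45 would imply 0.5.
- d+ and d−: abatacept-minus-placebo effect in positives and negatives. Not in the SAP; assumed 0 to 10.
- q+ and q−: probability of abatacept in the intervention arm for positives and negatives. In the control arm both are 0.5.

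Randomisation gives the two arms the same expected biomarker mix, so prognosis cancels:

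expected difference (1+2 minus 3+4) = p × d+ × (q+ − 0.5) + (1 − p) × d− × (q− − 0.5)

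**Section 2.4: q+ = q− = 0.5.** Both terms vanish. The difference is 0 for every p, d+ and d−. The same holds for every endpoint listed in section 6.1.2, because the arms do not differ in treatment.

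**Section 2: q+ = 1, q− = 0.5.** The difference is 0.5 × p × d+, and d− drops out. The abatacept share in the intervention arm is 0.5 + 0.5p, against 0.5 in control. With d+ = 10:

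| p | Abatacept share, intervention | Expected difference | Power, 90 per arm |
|---|---|---|---|
| 0.3 | 65% | 1.5 | about 10% |
| 0.5 | 75% | 2.5 | about 21% |
| 0.7 | 85% | 3.5 | about 37% |

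Power for 2.5 points: standard error = 14.34 × √(2/90) = 2.14; 2.5 / 2.14 = 1.17; 1.17 − 1.96 = −0.79, a normal probability of about 0.21. With d+ = 5 the differences are 0.75, 1.25 and 1.75.

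**What the section 2 contrast contains.** Let A = p × d+ + (1 − p) × d− be the average abatacept effect. Then

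0.5 × p × d+ = 0.5 × p × A + 0.5 × p × (1 − p) × (d+ − d−).

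The first term is what the same extra abatacept would yield if given at random; the second is the gain from targeting. At p = 0.5:

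- d+ = 10, d− = 10 (uninformative biomarker): A = 10; 2.5 + 0 = 2.5.
- d+ = 10, d− = 0 (fully predictive): A = 5; 1.25 + 1.25 = 2.5.

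The same total can be all extra drug or half targeting, and the contrast alone cannot show which.

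**Dependence on what is held fixed.** With A fixed at 5 and p = 0.5, the contrast is 1.25 when d+ = d− = 5, 1.875 when d+ = 7.5 and d− = 2.5, and 2.5 when d+ = 10 and d− = 0. On that scale it does grow with prediction.

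**The case against.** Four points can be made for the plan.

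1. *The objective concerns the policy, not the biomarker.* Under section 2 the contrast is a valid randomised comparison of the whole policy, extra abatacept included, with 1:1 allocation. This stands. A reader might infer that the objective fails under either allocation; the SAP does not support that. Under section 2 the limit is on interpretation.
2. *The contrast does respond to prediction.* A reader might infer that under section 2 the result is the same whether or not the biomarker predicts response. That is true only with d+ held fixed. With the average effect held at 5 and p = 0.5, it moves from 1.25 to 2.5.
3. *The groups may not be the arms.* The scheme diagram was not available, and the text is inconsistent. If Group 1 were positive on abatacept, 2 negative on placebo, 3 negative on abatacept and 4 positive on placebo, equal groups would give 0.5 × (d+ − d−), which does measure prediction. If 1+2 were all positive and 3+4 all negative, the contrast would be non-randomised and would include prognosis; section 2.3 reports a difference of 10 on methotrexate alone. Both conflict with objective III, which names the control and intervention arms. The arm reading fits objectives I to III best, but the result is conditional on it.
4. *The secondary analyses carry little weight.* Section 6.1.2 says the secondary endpoints are reported descriptively within groups, and section 6.7.1 uses them to support the primary endpoint, not as separate claims. The trial is powered for Group 1 vs 3 only. This lowers the consequence, but section 6.1.2 still lists the contrast and section 6.7.1 still applies the 5% level.

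**Conclusion.** The point holds, conditional on Groups 1+2 and 3+4 being the randomised arms. Under section 2.4 as written, the expected difference is exactly zero whatever the prevalence or drug effects, so the contrast cannot assess the strategy. Under section 2, if positives in the intervention arm all receive abatacept (implied, not stated), it is 0.5 × p × d+. That compares the policy validly with 1:1 allocation, but it does not involve the effect in negatives, is positive for an uninformative biomarker whenever abatacept works, and cannot separate targeting from greater drug use. The CDAI figures rest on assumed prevalence and effects.

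The comparator label is unsupported under either allocation. The point must be settled before analysis if section 2.4 is the operating allocation, and is less serious if section 2 is. Which allocation is right is not for this review to say.

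**What to change.** 1. Reconcile the allocation texts in sections 2 and 2.4, and define Groups 1 to 4 once by arm, biomarker status and treatment. Bring sections 2.1, 2.3, 6.1.1 and 6.1.2 into line.
2. If section 2.4 is the allocation, remove 1+2 vs 3+4 as a test of the strategy from objective III and section 6.1.2. If section 2 is, keep it as intervention policy vs random 1:1 allocation, and state that it does not isolate the biomarker's contribution.
3. In either case, base any conclusion on the biomarker's added value on the contrast already described in section 6.1.1: the abatacept-placebo difference in positives minus that in negatives (d+ − d−). Estimate it from all randomised patients with a 95% CI. It may be scaled by p × (1 − p), which expresses the gain from giving abatacept to positives only over giving the same share at random. With p treated as fixed, the test is the same. This is an interpretive scale, not an allocation that the SAP describes.
4. Replace the reference to clinical practice with a description of the actual control: random 1:1 abatacept or placebo, with methotrexate.

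The cost is SAP wording and reporting of one contrast. No patients or procedures are added, since objective II already presupposes biomarker status in control patients. The sponsor loses the claim against clinical practice, and the interval for d+ − d− will be wide.

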2.2 Study scheme diagram

The primary outcome will be assessed at 16 weeks from baseline.

2.3 Sample size determination

The primary aim of the study is to demonstrate that patients in the "Drug target biomarker" group (Group 1) will have a higher response rate than the "No drug target biomarker" groups (Group 2 and 3)- see section 2.2 for trial diagram.

Using change in CDAI score from baseline (delta CDAI) as the primary outcome, a difference in delta CDAI between the two comparison groups of 10, with a Standard Deviation of 14.34. These are the values that were observed when analysing the difference in delta CDAI between biomarker positive and biomarker negative patients treated with MTX in the PEAC study. Although PEAC patients were not treated with Abatacept, this comparison is expected to be even more in favour of the biomarker positive group using Abatacept together with MTX. Thus, basing the power calculation on the PEAC observed difference is a conservative assumption.

With these assumptions, 90 patients would be needed to detect a significant difference of 10 in delta CDAI with 90% power. Since this would only be for Group 1 and Group 3 (45 patients each), a total of 180 patients would be sufficient for 90% power in the whole trial (Figure 1 Section 2.6). If we assume a 5% dropout rate and also account for an expected 5% of patients that have insufficient RNA for the Nano-string analysis (based on results from the STRAP trial), 200 patients in the whole trial would be sufficient to detect a significant difference (Group 1 vs Group 3) of 10 in delta CDAI with 90% power.

All power calculations were performed using the "twomeans" package in STATA, version SE 18.

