6.1 Main analyses

6.1.1 Primary endpoint

The primary endpoint of the study will be a continuous outcome of CDAI measure at 16 weeks (visit 7).

The primary analysis will assess the difference in the CDAI comparing the difference in response between the abatacept and placebo groups with the biomarker positive group against the difference in response between the abatacept and placebo groups with the biomarker negative group. This analysis will be on an ITT basis according to original randomisation allocation.

The differences between the groups on the primary outcome will be tested with a mixed-effects model with time as a continuous variable. The CDAI is measured at five time points: (1) Baseline, (2) 4 Weeks, (3) 8 Weeks, (4) 12 Weeks, (5) 16 Weeks. The baseline measurement for the primary outcome is the CDAI score after randomisation. This measurement will be included in the analysis as a covariate.

The mixed-effects model results will be presented as P values and 95% CI. In the mixed-effects model we will use both an 'unstructured' and a '1. order autoregressive' covariance matrix and choose the matrix resulting in the lowest Bayesian information criterion. To assess, if the underlying assumptions behind the mixed-effects model analysis are fulfilled, we will investigate normal quantile plots of residuals, standardized residuals, and random effects. If the underlying assumptions behind the mixed-effects model analysis are clearly violated then we will use a generalized estimation equation for the analysis.

The planned primary analysis is a mixed-effects model adjusted for centre and patient comparing the outcome of CDAI between treatment groups in the biomarker arm (Group 1) and non-biomarker arms (Group 3).

A p-value of less than 0.05 will be taken to indicate statistical significance.

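### The powered primary contrast (Group 1 vs Group 3) cannot on its own show that the biomarker informs response to abatacept, and SAP section 6.1.1 also names a second, unpowered primary estimand

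*SAP*

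**What the plan says.** SAP section 2.1 sets the primary objective: to "determine whether synovial molecular profiles (=drug target signatures) can inform treatment response to abatacept in early RA". It answers this by comparing the 16-week change in CDAI "between the biomarker positive and the biomarker negative patients within the abatacept group (i.e. Group 1 vs Group 3").

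Section 2.3 powers only that contrast. It assumes "a difference in delta CDAI between the two comparison groups of 10, with a Standard Deviation of 14.34" and says that these values are the "difference in delta CDAI between biomarker positive and biomarker negative patients treated with MTX in the PEAC study". It acknowledges that the source patients had no abatacept and expects a larger gap with it: "Although PEAC patients were not treated with Abatacept, this comparison is expected to be even more in favour of the biomarker positive group". It concludes: "Thus, basing the power calculation on the PEAC observed difference is a conservative assumption". On these inputs "90 patients would be needed to detect a significant difference of 10 in delta CDAI with 90% power", which is 45 in each of Groups 1 and 3, 180 in the whole trial, and 200 after losses.

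Section 2.4 randomises patients 1:1 to abatacept or placebo within each biomarker stratum, all on methotrexate.

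Section 6.1.1 first describes the primary analysis as the abatacept-placebo difference in biomarker-positive patients set against the same difference in biomarker-negative patients. Later in the same section, the planned primary model compares Group 1 with Group 3. Neither the secondary objectives in section 2.1 nor the comparisons listed in section 6.1.2 include a treatment-by-biomarker interaction.

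**The concern.** Whether a biomarker informs response to a drug depends on whether the drug's benefit over its comparator differs by biomarker status. When both groups receive abatacept plus methotrexate, a gap between them has two possible sources: biomarker-positive patients may do better on methotrexate anyway, or they may gain more from abatacept. Group 1 vs Group 3 cannot tell these apart.

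The SAP gives its own reason to take the first source seriously, because its planning difference was observed without abatacept. A significant primary result could be reported as showing that the signature selects abatacept responders when a similar gap exists on placebo plus methotrexate. The placebo patients needed to check this are in the trial, but the planned Group 1 vs Group 3 model does not use them.

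**Working it through.** **Inputs.** Difference 10, SD 14.34, 90% power, 45 per group, losses of 5% and 5% (section 2.3); two-sided 0.05 (section 6). The calculations use unadjusted comparisons of means, as a two-means power calculation does, and take no credit for baseline adjustment or repeated measures.

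**Reproducing the plan.**
- Normal approximation: n per group = 2 × (1.960 + 1.282)² × 14.34² / 10² = 43.2, so 44. The noncentral t gives 45 per group, 90 in all, as stated.
- Power at 45 per group is 90.5% (t) or 91.1% (normal).
- Losses: 180 / 0.90 = 200, or 180 / (0.95 × 0.95) = 199.4. The stated 200 reproduces.

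**What each contrast estimates.** Let P be the biomarker-positive minus biomarker-negative difference on placebo plus methotrexate, and let I be the difference between the two strata in abatacept benefit over placebo.
- Group 1 − Group 3 = P + I.
- The difference of abatacept-placebo differences = I.

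The two agree only if P = 0.

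**Group 1 vs Group 3 when I = 0.** SE = 14.34 × √(2/45) = 3.02, 88 degrees of freedom. The noncentrality is P / 3.02.

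| Gap carried over (P) | Noncentrality | Chance of a significant result |
|---|---|---|
| 2.5 | 0.83 | 12.9% |
| 5 | 1.65 | 37.3% |
| 7.5 | 2.48 | 68.9% |
| 10 | 3.31 | 90.5% |

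A simulation of 50,000 trials with P = 10 and the same abatacept effect in both strata gave 90.5% for Group 1 vs Group 3. The interaction contrast rejected in 4.96%, its nominal rate.

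**Interaction contrast at the planned size.** This assumes four cells of 45. That needs about 50% biomarker positivity, which the SAP does not state.
- SE = 14.34 × √(4/45) = 4.28, against 3.02 for Group 1 vs Group 3.
- Power is 64% for I = 10 (noncentrality 10 / 4.28 = 2.34) and 21% for I = 5.
- Effect detectable with 90% power: 3.24 × 4.28 = 13.9.
- For 90% power at I = 10: 4 × (1.960 + 1.282)² × 14.34² / 10² = 86.4, so 87 per cell or 348 evaluable. After the SAP's losses this is 348 / 0.9025 = 386 to 348 / 0.90 = 387, against 200 planned.

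**The case against.** The strongest reply is that Group 1 vs Group 3 is a disclosed first step. Section 2.1 says the sponsor wants to establish a difference in response in the biomarker arm first, and section 3.3.1 defines a responder by a fall in CDAI, not by benefit over placebo. For the null hypothesis of that contrast, a significant result when the true gap is 10 is a correct rejection, and the 5% rate belongs to a different null. This stands, and it is why limiting the claim is an adequate remedy. It does not rescue the objective as worded, which concerns response to abatacept.

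A second reply is that section 6.1.1 already contains the right contrast. It does, but that contrast conflicts with sections 2.1 and 2.3 and with the planned model in 6.1.1 itself, and no power is given for it.

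Three stronger readings are tempting, and the document does not support them:
- A reader might infer that the plan has a 90% false-positive rate. That figure needs the full 10-point gap to appear on placebo plus methotrexate. The SAP uses 10 as a floor for the abatacept comparison and never states what the gap is on placebo. The trial also enrols inadequate responders to conventional DMARDs, which makes full carry-over uncertain.
- A reader might infer that the SAP wrongly claims intention-to-treat protection for Group 1 vs Group 3. The sentence "This analysis will be on an ITT basis according to original randomisation allocation" directly follows the description of the interaction contrast, which randomisation within strata does support.
- A reader might put a figure on the same problem in the secondary comparison of Group 1 with Groups 3 and 4. The group labels prevent it. Section 2.1 treats Group 3 both as biomarker-negative patients on abatacept and as part of the control arm, section 2.3 pairs it with Group 2, and biomarker prevalence is not given.

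**Conclusion.** The concern holds in this form: the powered contrast does not isolate what the primary objective asks, and section 6.1.1 carries two incompatible primary estimands. With no interaction at all, the chance of a significant Group 1 vs Group 3 result is 13% to 90.5% for carried-over gaps of 2.5 to 10 points. The top figure is conditional on full carry-over. A smaller gap lowers the rate but does not separate prognosis from prediction.

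These figures rest on 45 per group, SD 14.34, no covariate gain, and the explicit statement in section 2.1 that both groups receive abatacept.

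The claim that the planning value is conservative is unsupported. It comes from response to methotrexate, whereas section 2 describes patients with an inadequate response to conventional DMARDs, and no argument is given that the gap persists or grows in them.

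A reader might also conclude that the interaction has to become the primary test. That does not follow: at the planned size it is a real trade-off, and either choice can be defended if the claim matches the contrast.

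**What to change.** 1. Reconcile sections 2.1, 2.3 and 6.1.1 to one primary estimand, with consistent group definitions.
2. If Group 1 vs Group 3 stays primary, state that it shows only an association between biomarker status and outcome on abatacept plus methotrexate.
3. Pre-specify one model with a treatment-by-biomarker term on all randomised patients. Report the biomarker difference on placebo plus methotrexate and the interaction, each with a 95% CI, beside the primary result.
4. Base any statement that the biomarker informs abatacept response on the interaction.
5. Delete the sentence in section 2.3 that calls the planning difference conservative.
6. State in section 2.3 that the 90% power applies only to Group 1 vs Group 3, and give the interaction's precision and power with the assumed cell sizes.

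The work is SAP wording and one model term, on patients the trial already randomises. The real cost is precision: the interaction would be estimated with limited power, and an inconclusive result on the predictive question is quite possible at 200 patients.
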